2.5. Efficacy, Pharmacokinetic, and Safety Variables

2.5.1. Efficacy Variables

- Objective Response Rate (ORR) defined as the percentage of patients who have at least one confirmed partial response (PR) or complete response (CR) according to Response Evaluation Criteria in Solid Tumors (RECIST) v.1.1
- Disease Control Rate (DCR) defined as the percentage of patients with a response of CR, PR or stable disease (SD) according to RECIST v.1.1
- Progression Free Survival (PFS) defined as the time from the first study treatment to the first occurrence of progression, as measured by RECIST v.1.1 or death from any cause, whichever occurs first
- Overall survival (OS) defined as the time from first study treatment to death from any cause.
- Duration of stable disease (DOSD) defined as the time from the first occurrence of stable disease or better (PR or CR or SD) to the time of the first documented disease progression or death from any cause, whichever occurs first per RECIST v.1.1

2.5.2. Pharmacokinetics and Pharmacodynamics Variables

To evaluate the pharmacokinetics of NT-17 administered in combination with atezolizumab:

- Serum concentration of NT-17 will be used to estimate the following parameters: Area under the concentration time-curve (AUC), Maximum serum concentration (C_{max}), Minimum serum concentration (C_{min}), Clearance (CL) to be completed by Third Party Vendor.

To evaluate the immunogenicity of NT-17, the following endpoint will be analyzed:

- Incidence of anti-drug antibody (ADA) to NT-17 during the study relative to prevalence of ADA at baseline, defined as ADA titer relative to baseline to Day 1 of each cycle.

To evaluate the effect of the investigational treatment combination on the tumor microenvironment, based upon baseline and post-baseline tumor biopsy, the following endpoints will be assessed, but are outside of the scope of this plan:

- Number, distribution, and phenotype of tumor-infiltrating cells
- Expression of Interferon γ (IFN γ) and associated inflammatory gene expression in the tumor microenvironment

Sponsor:	NeolimmuneTech, Inc.		
Protocol:	NIT-106 (ION-02)		
Document Version No.:	1.0	Document Date:	20Nov2023

- Changes in tumor microenvironment that correlate with response or provide information on potential actionable causes for lack of clinical benefit

Potential correlation with PK, pharmacodynamics (PD), safety, and efficacy parameters can be explored but are outside of the scope of this plan.

2.5.3. Safety Variables

To confirm the safety and tolerability of the following safety variables:

- Adverse Events (AE) incidence, nature, and severity of AEs graded according to NCI CTCAE v5.0
- Clinical Laboratory Assessments (CBC and serum chemistry)
- Physical Examinations
- Vital signs
- Electrocardiograms (ECG)
- Eastern Cooperative Oncology Group (ECOG) Performance Status

Sponsor:	NeolimmuneTech, Inc.		
Protocol:	NIT-106 (ION-02)		
Document Version No.:	1.0	Document Date:	20Nov2023

3. PATIENT POPULATIONS

3.1. Population Definitions

The following patient populations will be evaluated and used for presentation and analysis of the data:

3.1.1. Safety Population

The Safety Population will include all patients who receive at least 1 dose of the investigational regimen. The Safety Population will be the primary set for the analysis of safety and non-efficacy data.

3.1.2. Efficacy Population

The efficacy analysis will be conducted on all patients who received at least one cycle of study treatment and have at least one evaluable post baseline tumor assessment.

The efficacy population will be used for all efficacy analysis.

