11. MEASUREMENT OF EFFECT

11.1 Antitumor Effect – Solid Tumors

For the purposes of this study, patients should be re-evaluated for response every 9 weeks for the first two timepoints, then at least every 12 weeks as per standard of care.

Response and progression will be evaluated in this study using the new international criteria proposed by the revised RECIST guideline (version 1.1) [48](#). RECIST 1.1 will be used as the primary measure for assessment of tumor response, date of disease progression, and as the basis for all protocol guidelines related to disease status (e.g., discontinuation of study treatment). Changes in the largest diameter (unidimensional measurement) of the tumor lesions and the shortest diameter in the case of malignant lymph nodes are used in the RECIST criteria.

This study will also evaluate response and progression using immune-related RECIST (iRECIST) criteria. Investigators should note the different requirements for confirmatory scans as well as follow up of the two criteria.

11.1.1 *Definitions*

Evaluable for toxicity. All patients will be evaluable for toxicity from the time of their first treatment with atezolizumab and/or NT-I7 until 30 days after the last dose of study treatment.

Evaluable for objective response. Only those patients who have measurable disease present at baseline, have received at least 1 cycle of therapy and have had their disease re-evaluated will be considered evaluable for response. These patients will have their response classified according to the definitions stated below. (Note: Patients who exhibit objective disease progression before the end of cycle 1 will also be considered evaluable.)

Evaluable Non-Target Disease Response. Patients who have lesions present at baseline that are evaluable but do not meet the definitions of measurable disease, have received at least 1 cycle of therapy and have had their disease re-evaluated will be considered evaluable for non-target disease. The response assessment is based on the presence, absence or unequivocal progression of the lesions.

11.1.2 *Disease Parameters*

Measurable disease. Measurable lesions are defined as those that can be accurately measured in at least 1 dimension (longest diameter to be recorded) as ≥ 20 mm (≥ 2 cm) by chest x-ray or as ≥ 10 mm (≥ 1 cm) with CT scan, MRI or calipers by clinical exam. All tumor measurements must be recorded in millimeters (or decimal fractions of centimeters).

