Based on the available data provided in Section 2.2, the average historical ORR for the patients in this study would be 45.25% in Arm I and less than 5% in Arm II. With a total of 24 patients treated at the RP2D in Phase 2a of the study in Arm I, the 95% confidence interval for an observed ORR of 17/24 or higher would exclude 45.25%. With a total of 36 patients treated at the RP2D in Phase 2a of the study in Arm II, the 95% confidence interval for an observed ORR of 6/36 or higher would exclude 5%.

Approximately 84 patients will be enrolled in this study; up to approximately 24 patients in the Phase 1b and approximately 60 evaluable patients in the Phase 2a of the study. The expected accrual is 4 patients per month total at approximately 8 ION sites.

Safety Population: All patients who receive at least 1 dose of the investigational regimen will be considered evaluable for safety and included in the overall safety analysis. For the Phase 1b, in the absence of a DLT, patients must complete the full 3-week DLT window period to be considered evaluable for DLTs. Patients who discontinue from the study before the completion of the full 3-week (21 days) DLT window for reasons other than the occurrence of a DLT (e.g., withdrawal of consent, rapid tumor progression, death due to rapid tumor progression, AE that does not meet DLT criteria) will not be considered evaluable for DLTs and will be replaced.

Efficacy Population: The efficacy analysis for the Phase 1b (dose escalation) portion will be conducted on all DLT-evaluable patients, as defined in Section 6.2.2. The efficacy analysis for the Phase 2a (expansion phase) portion will be conducted on all patients who received at least one cycle of study treatment and have at least one evaluable post baseline tumor assessments.

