15.6 Reporting and Exclusions

15.6.1 Evaluation of Toxicity

All patients will be evaluable for toxicity from the time of their first treatment with atezolizumab and/or NT-I7 until 30 days after the last dose of study treatment.

15.6.2 *Evaluation of Response*

All patients enrolled in the study who received at least 1 cycle of study treatment will be assessed for response to treatment, even if there are major protocol treatment deviations or if they are ineligible. Each patient will be assigned one of the following categories: (1) CR, (2) PR, (3) SD, (4) PD, (5) early death from malignant disease, (6) early death from toxicity, (7) early death because of other cause, or (9) unknown (not assessable, insufficient data). [Note: By arbitrary convention, category 9 usually designates the “unknown” status of any type of data in a clinical database.]

All of the patients who met the eligibility criteria and received at least 1 dose of study treatment will be included in the main analysis of the response rate. Patients in response categories 4-9 should be considered to have a treatment failure (disease progression). Thus, an incorrect treatment schedule or drug administration does not result in exclusion from the analysis of the response rate. Precise definitions for categories 4-9 will be protocol specific.

All conclusions should be based on patients who received at least 1 cycle of study treatment. Sub-analyses may then be performed on the basis of a subset of patients, excluding those for whom major protocol deviations have been identified (early death due to other reasons, early discontinuation of treatment, major protocol violations, *etc.*). However, these sub-analyses may not serve as the basis for drawing conclusions concerning treatment efficacy, and the reasons for excluding patients from the analysis should be clearly reported. The 95% confidence intervals should also be provided.

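### The efficacy set requires a post-baseline scan that protocol 15.6.2 does not, so patients it counts as failures leave the ORR and DCR denominators and OS is conditioned on reaching a scan

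*SAP*

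**What the plan says.** The two documents define the patients for efficacy in several ways.

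- **SAP 3.1.2:** "all patients who received at least one cycle of study treatment and have at least one evaluable post baseline tumor assessment". The section applies this to all efficacy analysis and names no phase.
- **Protocol 15.3, Phase 2a:** the same rule, "conducted on all patients who received at least one cycle of study treatment and have at least one evaluable post baseline tumor assessments".
- **Protocol 15.3, Phase 1b:** "The efficacy analysis for the Phase 1b (dose escalation) portion will be conducted on all DLT-evaluable patients", with no scan condition.
- **Protocol 15.6.2, main response-rate analysis:** "All of the patients who met the eligibility criteria and received at least 1 dose of study treatment will be included in the main analysis". Categories 4 to 9 (progression, three kinds of early death, unknown) are treatment failures.
- **Protocol 15.6.2, basis for conclusions:** "All conclusions should be based on patients who received at least 1 cycle of study treatment", again with no scan condition.
- **Protocol 11.1.1:** response-evaluable patients need measurable disease, one cycle and a re-evaluation, but "Patients who exhibit objective disease progression before the end of cycle 1 will also be considered evaluable".

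SAP 4.8.1 classes patients without post-baseline assessments as not evaluable (NE). SAP 1.2.3 promises to outline differences from the protocol. SAP section 5 lists, among the changes due to premature closure, that efficacy summaries use the Efficacy Population only. SAP 4.4 tabulates disposition and the reasons for stopping treatment or leaving the study. It has no table of who is excluded from the Efficacy Population and why.

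**The concern.** ORR is the protocol's Phase 2a primary endpoint, and its denominator is defined in incompatible ways. The contradiction starts inside the protocol, between 15.3 and 15.6.2. The SAP follows 15.3, extends the scan rule to Phase 1b and applies it to OS as well.

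The patients affected are those who stop or die before a scan. Protocol 15.6.2 keeps them as failures if they are eligible. SAP 3.1.2 removes them, so the NE row in SAP 4.8.1 cannot hold the patients without a post-baseline assessment for whom it was written. Through the scan condition, ORR and DCR can only go up or stay at zero. OS runs from Cycle 1 Day 1, but entry depends on something that happens later.

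**Working it through.** **1. The plan's own benchmarks.** Protocol 15.3 and SAP 4.1 say that 17/24 excludes 45.25% and 6/36 excludes 5%. Exact (Clopper-Pearson) 95% intervals reproduce both:

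- 17/24: 48.9% to 87.4%. 16/24: 44.7% to 84.4%, which does not exclude 45.25%.
- 6/36: 6.4% to 32.8%. 5/36: 4.7% to 29.5%, which does not exclude 5%.

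Both documents state these for 24 and 36 *treated* patients. If one of 24 is dropped, 16/23 (69.6%, lower limit 47.1%) excludes 45.25%, while the same 16 responders among 24 treated (66.7%, lower limit 44.7%) do not. If three of 36 are dropped, 5/33 (lower limit 5.1%) excludes 5%, while 5/36 (lower limit 4.7%) does not. The numbers dropped are assumptions. The SAP's efficacy output pools by dose rather than by arm, so this shows sensitivity and does not reproduce a planned table.

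**2. Direction for ORR and DCR.** ORR needs a confirmed CR or PR. Protocol 11.1.4.3 needs SD documented more than 4 weeks from baseline. A patient with no evaluable post-baseline scan can be none of these. If k of n are dropped for that reason, the numerator stays and the rate is multiplied by n/(n−k) = 1/(1−d), where d = k/n. A zero stays at zero.

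| Assumed d | Factor |
|---|---|
| 5% | 1/0.95 = 1.05 |
| 10% | 1/0.90 = 1.11 |
| 20% | 1/0.80 = 1.25 |

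Group sizes after closure are not given. With an assumed 20 treated:

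| Assumed result | None dropped | 2 dropped | 4 dropped |
|---|---|---|---|
| DCR, 9 patients | 9/20 = 45.0% | 9/18 = 50.0% | 9/16 = 56.3% |
| ORR, 3 patients | 3/20 = 15.0% | 3/18 = 16.7% | 3/16 = 18.8% |

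The pooled 120/360/840 µg/kg group is planned at 3 levels × 3 to 6 = 9 to 18 DLT-evaluable patients. One dropped patient gives 9/8 = 1.125 or 18/17 = 1.06.

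Two other differences can move the rate either way. The SAP requires a full cycle where 15.6.2's main set requires one dose, and it keeps ineligible patients whom that set omits.

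**3. The window.** Protocol 11.1 says "patients should be re-evaluated for response every 9 weeks for the first two timepoints", and protocol 6.7 allows ±1 week, so the first scheduled scan falls on days 56 to 70. Cycle 1 ends on day 21. That leaves 56−21 = 35 to 70−21 = 49 days in which a patient who completed cycle 1 can die unscanned.

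**4. OS.** Three months is 3 × 30.4375 = 91.3 days (SAP 4.2.11). A patient first scanned on schedule has already survived 56/91.3 = 61% to 70/91.3 = 77% of the period behind the planned 3-month rate. Ignoring censoring, if S is the true survival and a is the share of dropped patients alive at that time, the reported rate is (S − d·a)/(1 − d).

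| Assumed S | d | a | Reported |
|---|---|---|---|
| 85% at 3 months | 10% | 0.85 | 85.0% |
| 85% at 3 months | 10% | 0.50 | 88.9% |
| 85% at 3 months | 10% | 0 | 94.4% (upper bound) |
| 85% at 3 months | 5% | 0 | 89.5% (upper bound) |
| 50% at 12 months | 10% | 0.50 | 50.0% |
| 50% at 12 months | 10% | 0 | 55.6% (upper bound) |

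No direction is claimed for PFS. It also depends on how the censoring rules in SAP Table 1 would treat an unscanned patient.

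**5. How far the end-of-treatment scan helps.** Protocol 6.6 asks for one 30±5 days after the last dose, unless an assessment was done within the past 9 weeks (63 days) for patients on study up to 18 weeks. Baseline imaging may be up to 28 days old at first dose. After a single dosing day, the baseline scan is at most 28+35 = 63 days old at that visit, so if it counts, no new scan is required. With a second dose 21 days later, it is 46 to 84 days old (21+25 to 28+21+35), so some patients would be scanned.

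**The case against.** The strongest defence is that the SAP follows the protocol's own named Efficacy Population for Phase 2a, where 15.3 also speaks of 60 evaluable patients. Protocol 11.1.1 likewise ties evaluability to re-assessment. On this view 15.6.2 is unadapted template text: it leaves categories 4 to 9 to be defined and never defines them. That explains where the SAP rule came from, but it does not resolve the conflict. Protocol section 15 says no separate SAP would be issued, so 15.6.2 is part of the pre-specified plan.

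Disclosure is partial, not absent, because SAP section 5 states the restriction. It does not mention the failure rule or the Phase 1b set.

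Materiality is limited. No p-values are planned, and the study closed early with few responses. In the example above, exact 95% intervals are 3.2% to 37.9% for 3/20 and 3.6% to 41.4% for 3/18, so a two-patient loss is small beside the sampling error. Nothing in the documents shows that anyone was dropped. End-of-treatment and 12-weekly follow-up scans should capture some early stoppers.

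A reader might infer that early deaths could not be told apart from withdrawals. The documents do not support that. The SAP plans by-patient listings of deaths (4.11.1), tumor assessments (4.8.1) and study completion with withdrawal reason (4.4). Protocol 15.6.2 also asks that exclusion reasons be reported, in its sentence on sub-analyses. Only a summary table is missing.

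A reader might also infer that a protocol amendment is required. Protocol section 15 ties amendments to changes in primary or key secondary hypotheses, or methods related to them, made before any analysis. The documents do not settle whether this change qualifies.

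**Conclusion.** The conflict is real and should be fixed. Neither set in protocol 15.6.2 has a scan condition. Protocol 15.3 (Phase 2a) and SAP 3.1.2 (both phases, every efficacy endpoint) do, and section 5 does not reconcile them.

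For ORR and DCR the direction of the scan condition is certain: upward if at least one treated patient is dropped for lack of a scan and the numerator is above zero. The size, 1.05 to 1.25 times, rests on assumed losses of 5% to 20%.

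For OS, upward bias is expected only if dropped patients die earlier than the rest. The range from no change to 94.4% against a true 85% depends on assumed values, and its top requires every dropped patient to have died within three months.

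The documents do not show that any reported result is in fact inflated.

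**What to change.** - **SAP 3.1.2 and 4.8.1:** report ORR and DCR by pooled dose group on all treated patients, already defined as the Safety Population in 3.1.1. Count NE, unknown and early death as non-response. Flag ineligible patients so that the eligible set of protocol 15.6.2 can also be shown.
- **SAP 4.8.2 and 4.8.3:** run PFS and OS on all treated patients from Cycle 1 Day 1. This is a recommendation of this review, since 15.6.2 covers response only.
- **Current Efficacy Population:** keep it as a labelled sensitivity analysis.
- **SAP 4.4:** add a short table of exclusions from that set by dose group and reason.
- **SAP section 5:** state how protocol 11.1.1, protocol 15.3 (both phases), both sets in protocol 15.6.2 and SAP 3.1.2 are reconciled.

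The cost is wording, one extra efficacy table and a few disposition rows, with no new data. Reported ORR and DCR may be slightly lower.

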3.1.3. Pharmacokinetic (PK) Population

The PK Population will include all patients who receive at least 1 dose of the investigational regimen and have at least 1 non-missing PK sample available for analysis.

The PK Population will be used for the PK analysis.

3.2. Protocol Violations

Violations of the protocol will be collected and reported. The sponsor, or designee, will be responsible for producing the final protocol violation file (formatted as a Microsoft Excel file), in collaboration with Cytel.

All protocol violations will be presented in the data listings.

Sponsor:	NeolimmuneTech, Inc.		
Protocol:	NIT-106 (ION-02)		
Document Version No.:	1.0	Document Date:	20Nov2023

4. STATISTICAL METHODS

4.1. Sample Size Justification

During the dose escalation phase (Phase 1b), a 3+3 design will be used for identifying the MTD and/or the RP2D. The following design will be used:

Number of Patients with Dose-Limiting Toxicity (DLT) at a Given Dose Level	Escalation Decision Rule
0 out of 3	Enroll 3 patients at the next dose level.
1 out of 3	Enroll at least 3 more patients at this dose level. 
- If 0 of these 3 additional patients experience a DLT (totaling 1/6), enroll at the next dose level.- If ≥ 1 of these 3 additional patients experiences DLT (totaling $\geq 2/6$ at the dose level), the dose escalation is stopped, and the next lower dose level will be declared the MTD. In the case this happens at the 120 $\mu\text{g}/\text{kg}$ dose level, a lower dose of 60 $\mu\text{g}/\text{kg}$ will be tested, and the same 3+3 design followed.
≥ 2 out of 3	Dose escalation will be stopped. The next lower dose level will be declared the MTD. Three (3) additional patients will be entered at the next lower dose level if only 3 patients were treated previously at that dose. In the case this happens at the 120 $\mu\text{g}/\text{kg}$ dose level, a lower dose of 60 $\mu\text{g}/\text{kg}$ will be tested, and the same 3+3 design followed.

Based on the available data (Section 2.2 of the protocol), the average historical ORR for the patients in this study would be 45.25% in Arm I and less than 5% in Arm II. With a total of 24 patients treated at the RP2D in Phase 2a of the study in Arm I, the 95% confidence interval for an observed ORR of 17/24 or higher would exclude 45.25%. With a total of 36 patients treated at the RP2D in Phase 2a of the study in Arm II, the 95% confidence interval for an observed ORR of 6/36 or higher would exclude 5%.

Sponsor:	NeolimmuneTech, Inc.		
Protocol:	NIT-106 (ION-02)		
Document Version No.:	1.0	Document Date:	20Nov2023

Approximately 84 patients will be enrolled in this study; up to approximately 24 patients in the Phase 1b and approximately 60 patients in the Phase 2a of the study. The expected accrual is 4 patients per month total at approximately 8 ION sites.

4.2. General Statistical Methods and Data Handling

4.2.1. General Methods

All output will be incorporated into RTF or PDFs, sorted and labeled according to the International Conference on Harmonisation (ICH) recommendations, and formatted to the appropriate page size(s).

Phase 1b/dose escalation will be presented by dose levels 120 µg/kg, 360 µg/kg, 840 µg/kg, 1200 µg/kg and Total. Phase 2a/dose expansion will be summarized under the 1200 µg/kg dose. Efficacy analysis will analyze two groups of pooled data. The first group will pool 120 µg/kg, 360 µg/kg, and 840 µg/kg doses levels of Phase 1b; and the second group will pool the 1200 µg/kg dose level from both phases.

For categorical variables, summary tabulations of the number and percentage within each category (with a category for missing data) of the parameter will be presented.

Continuous variables will be summarized using mean, standard deviation, median, inter-quartile range (IQR) and range; 95% confidence intervals will be presented where appropriate.

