3. OBJECTIVES AND ENDPOINTS

This study will evaluate the safety and tolerability and assess the antitumor efficacy of NT-I7 in combination with atezolizumab (Phase 1b/2a) in patients with anti-PD-1/PD-L1 naïve or relapsed/refractory high-risk skin cancers (cSCC, MCC, melanoma). Specific objectives and corresponding endpoints for the study are outlined in Table 2.

Table 2 – Study Objectives and Endpoints

Objectives	Corresponding Endpoints
Primary Objective	

To evaluate the safety and tolerability of NT-I7 in combination with atezolizumab (Phase 1b), including estimation of the Maximum Tolerated Dose (MTD) and/or the Recommended Phase 2 Dose (RP2D)
 
Phase 2a: To evaluate the Objective Response Rate (ORR) according to RECIST v1.1 and iRECIST, as determined by the investigator
	
 - Incidence, nature, and severity of adverse events graded according to NCI CTCAE v5.0 - Incidence and nature of DLTs - Potential correlation with PK, pharmacodynamic, safety, and efficacy parameters - Objective Response Rate (ORR), defined as the percentage of patients who have at least one confirmed partial response (PR) or complete response (CR) according to RECIST v1.1 and iRECIST, as determined by the investigator
Secondary Objectives	

To evaluate immunogenicity of NT-I7 in combination with atezolizumab
 
To make a preliminary assessment of the anti-tumor activity of NT-I7 in combination with atezolizumab
	
 - Incidence of anti-drug antibody (ADA) to NT-I7 during the study relative to the prevalence of ADA at baseline - Disease Control Rate (DCR), defined as proportion of patients with a best overall response of CR, PR or stable disease (SD). - Duration of objective response (DOR), defined as the time from the first occurrence of a documented objective response to the time of the first documented disease progression or death from any cause, whichever occurs first, per RECIST v1.1 and iRECIST as determined by the investigator - Progression Free Survival (PFS), defined as the time from the first study treatment (Cycle 1, Day 1) to the first occurrence of progression or death from any cause, whichever occurs first, per RECIST v1.1 and iRECIST as determined by the investigator - Overall survival (OS), defined as the time from first study treatment (Cycle 1, Day 1) to death from any cause
Exploratory Objectives	

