15.4 Stratification Factors: N/A

15.5 Analysis of Secondary Endpoints

15.5.1 Secondary Objectives

Statistical analyses will be conducted for the following secondary objectives:

- The immunogenicity of NT-I7
- A preliminary assessment of the anti-tumor activity of NT-I7 in combination with atezolizumab, including the ORR, as measured by RECIST v1.1 and iRECIST, the DCR, DOR, PFS, and OS.

Descriptive statistics will be provided. Mean, standard deviation, median, minimum and maximum will be displayed for continuous variables, and numbers and percentages will be displayed for counts and binary variables. Kaplan-Meier estimates will be considered for time to event variables (DOR, PFS and OS). The analyses will be performed for each arm in Phase 2a, separately.

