2. STUDY DESIGN

2.1. Synopsis of Study Design

This is a Phase 1b/2a, open-label, multicenter study to evaluate the safety, tolerability and anti-tumor effect of NT-17 (recombinant human interleukin 7 [rhIL-7]-hybrid Fc [hyFc]) in combination with atezolizumab (MPDL3280A) in patients with anti-PD-1/PD-L1 naïve or relapsed/refractory high-risk skin cancers including cSCC, MCC and melanoma.

This study has been designed to allow for an investigation of MTD or RP2D of NT-17 in combination with atezolizumab. There are two phases to this study:

[figure not shown]
- Phase 1b, a NT-17 dose escalation phase to determine the MTD or RP2D
- Phase 2a, a non-randomized parallel dose expansion phase to confirm the MTD or RP2D in both arms

Arm I: Anti-PD-1/PD-L1 (checkpoint inhibitors [CPI]) naïve patients with cSCC and MCC
Arm II: Anti-PD-1/PD-L1 relapsed/refractory patients with MCC, cSCC and melanoma

Number of Patients

Approximately 84 patients will be enrolled; up to 24 patients will be enrolled in the Phase 1b (3 + 3 dose escalation design will be used), and approximately 60 patients will be enrolled in the Phase 2a (24 patients in Arm I, i.e., 12 patients for each indication, and 36 patients in Arm II, i.e., 12 patients for each indication).

Sponsor:	NeolimmuneTech, Inc.		
Protocol:	NIT-106 (ION-02)		
Document Version No.:	1.0	Document Date:	20Nov2023

Figure 1 Phase 1b\2a Schema

Each patient will participate in the trial ("enrolled") from the time the Informed Consent Form (ICF) is signed through final protocol-specified contact. The active study will end when the last patient completes the 90-day safety follow up visit, approximately 27 months after enrollment. Trial is expected to be completed approximately 36 months after the last patient is enrolled.

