4.2.6. Subpopulations

No analyses of subpopulations of patients are planned.

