4.7. Study Treatment

Dose intensities will be summarized based on the Safety Population, with phases 1b and 2a presented separately by dose level/arm. Patients who have completed each cycle will be summarized.

The dose intensity of NT-17 and atezolizumab is defined as:

Total actual dose received /duration of treatment(months); where treatment duration is last dose date – first dose date + 1

Dose intensity will be summarized overall for each product.

Study treatment data will be included in a by-patient listing.

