4.8.1. Objective Response Rate and Disease Control Rate

ORR is defined as the percentage of patients who have at least one confirmed partial response (PR) or complete response (CR) according to RECIST v1.1 as determined by the investigator.

DCR is defined as percentage of patients with a response of CR, PR or Stable Disease (SD) according to RECIST v1.1.

The best overall response (BOR) is the best response recorded from the start of the treatment until disease progression/recurrence. Patients without baseline or post-baseline assessments will be considered Not Evaluable (NE).

The number and percentage of patients in each BOR category (CR, PR, SD, PD, NE), and ORR and DCR will be presented.

Listings of tumor assessments and responses assessment will be provided.

Sponsor:	NeolimmuneTech, Inc.		
Protocol:	NIT-106 (ION-02)		
Document Version No.:	1.0	Document Date:	20Nov2023

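### The SAP pools both Phase 2a arms by dose for efficacy, so the primary ORR cannot be read against either arm's historical benchmark (45.25% and 5%)

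*SAP*

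**What the plan says.** Protocol section 3 (Table 2) sets the Phase 2a primary objective: "Phase 2a: To evaluate the Objective Response Rate (ORR) according to RECIST v1.1 and iRECIST, as determined by the investigator". The sample-size text in Protocol 15.3, repeated in SAP 4.1, states that "the average historical ORR for the patients in this study would be 45.25% in Arm I and less than 5% in Arm II". It then says that a 95% interval for 17/24 or more in Arm I would exclude 45.25%, and that one for 6/36 or more in Arm II would exclude 5%. The planned enrolment in SAP 2.1 is "24 patients in Arm I, i.e., 12 patients for each indication, and 36 patients in Arm II". Protocol 15.5.1, whose list of endpoints includes ORR, DCR, DOR, PFS and OS, says: "The analyses will be performed for each arm in Phase 2a, separately".

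SAP 4.2.1 takes another course: "Efficacy analysis will analyze two groups of pooled data". One group is the 120, 360 and 840 µg/kg cohorts of Phase 1b. The other is every 1200 µg/kg patient from both phases. SAP 4.2.6 adds: "No analyses of subpopulations of patients are planned". SAP 4.8.1 says: "The number and percentage of patients in each BOR category (CR, PR, SD, PD, NE), and ORR and DCR will be presented"; it names no grouping and no interval for ORR. SAP 4.8.2 to 4.8.4 plot PFS, OS and duration of stable disease by pooled dose.

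The arm variable is used elsewhere in the SAP. Dose intensity in SAP 4.7 is shown "with phases 1b and 2a presented separately by dose level/arm".

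**The concern.** The two arms are different populations. On the plan's own figures their expected response rates differ about nine-fold (45.25 / 5 = 9.05). Both dose pools mix naive with relapsed/refractory patients, since the Protocol 1.2 schema says each Phase 1b cohort includes both. The response rate of such a pool depends on its case mix as well as on the treatment.

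Two readings are at stake. The primary one is whether the ORR in each arm exceeds its own historical rate, and no planned efficacy summary shows this. The second is a reader's comparison of the lower-dose pool with the 1200 µg/kg pool, which is confounded by the share of naive patients in each.

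The SAP also handles the change poorly. Section 4.2.3 says that pooling does not apply, although 4.2.1 has just defined the pools. Section 5 lists the departures from the protocol and omits this one. Its nearest item, putting all phases in one table, concerns phases and layout, not arms.

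**Working it through.** **Inputs.** Benchmarks 45.25% and 5%, arm sizes 24 and 36, and thresholds 17/24 and 6/36 come from Protocol 15.3 and SAP 4.1. Neither document names the interval method; I used two-sided 95% Clopper-Pearson. For x responders in n, the lower limit is the 0.025 quantile of Beta(x, n−x+1) and the upper limit is the 0.975 quantile of Beta(x+1, n−x).

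**1. Reproduce the plan's thresholds.**

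| Arm | Responders | 95% CI | Excludes own benchmark? |
|---|---|---|---|
| I | 16/24 | 44.7–84.4% | no |
| I | 17/24 | 48.9–87.4% | yes (45.25%) |
| II | 5/36 | 4.7–29.5% | no |
| II | 6/36 | 6.4–32.8% | yes (5%) |

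Both stated thresholds are the exact minima. Of the methods tried (exact, Wilson, Agresti-Coull, Wald), only the exact interval gives both. At the benchmark rates, P(X ≥ 17 of 24) = 0.0102 and P(X ≥ 6 of 36) = 0.0083. The rules are therefore coherent when applied by arm.

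**2. Benchmark of the pooled group.** Pooled rate = (n₁ × 45.25% + n₂ × 5%) / (n₁ + n₂).

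- Planned 24:36: (24 × 45.25 + 36 × 5) / 60 = 1266 / 60 = 21.1%.
- With six Phase 1b patients added: 19.6% if all are relapsed/refractory (24:42), 23.3% if all are naive (30:36).
- With uneven accrual after early closure (assumed mixes): 10.75% at 6:36 and 37.2% at 24:6.

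The blended benchmark moves with case mix and equals neither arm's figure.

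**3. One pooled result, opposite arm conclusions** (full accrual, Phase 2a only). Pooled 18/60 = 30.0%, CI 18.9–43.2%.

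| Split | Arm I | Arm II |
|---|---|---|
| 17/24 + 1/36 | 48.9–87.4%, excludes 45.25% | 0.1–14.5%, does not exclude 5% |
| 8/24 + 10/36 | 15.6–55.3%, does not exclude 45.25% | 14.2–45.2%, excludes 5% |

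**4. The pool against each benchmark.**

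- If both arms just succeed, 17 + 6 = 23/60 = 38.3%, CI 26.1–51.8%. The pooled interval still contains 45.25%. Excluding it needs 36/60 (lower limit 46.5%; for 35/60 it is 44.9%).
- If both arms are exactly at their historical rates, the pooled lower limit exceeds 5% from 8/60 upwards (5.9%; for 7/60 it is 4.8%). Convolving Bin(24, 0.4525) with Bin(36, 0.05), P(X ≥ 8) = 0.973.

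So the pool can hide success against the higher benchmark, and it almost always appears to beat the lower one.

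**5. Comparing the dose pools.** Expected ORR with no added drug effect = f × 45.25% + (1 − f) × 5%, where f is the naive share. The documents do not give f for either pool, so these values are assumptions.

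- f = 30%: 17.1%.
- f = 36% to 45% (24/66 to 30/66, planned accrual plus six Phase 1b patients): 19.6% to 23.3%.
- f = 60%, possible only if accrual departs from plan: 29.2%.

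Against a pool at 30%, the spurious difference is 2.6 to 6.2 points at planned accrual and 12.1 points if the other pool reaches 60%.

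**The case against.** The strongest defence is early closure. SAP section 5 says the study ended prematurely and that responses were few. The 17/24 and 6/36 rules assume full arms; if an arm fell short, its rule could not be applied under any table layout. The 60-patient examples then describe a trial that may not have happened. The SAP is descriptive, plans no p-values and makes no formal dose comparison. SAP 4.8.1 does not state its grouping, and the table shells the SAP mentions are not in the supplied text. By-patient response listings are planned, so ORR by arm might be rebuilt by hand. On intervals, Protocol 15.6.2 asks for 95% intervals, and SAP 4.2.1 offers them where appropriate, though in its sentence on continuous variables.

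Much of this is fair as a limit on the numbers. The examples hold at full accrual only. The 60% naive share lies outside planned accrual. The benchmarks support interval-exclusion statements at fixed sizes, not a powered test. In addition, 45.25% does not follow exactly from the Protocol 2.2 table (simple averages give 45.33% or 45.75%, and the 17/24 threshold is unchanged at either). That table gives no relapsed/refractory rate.

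None of it restores the arm split. With few responses it matters more, not less, which arm they came from. A short arm is handled by reporting its actual n with an exact interval. A listing is not a planned analysis, and SAP 4.1 still carries two arm-specific rules that its own efficacy summaries cannot evaluate.

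**Conclusion.** The concern holds. The SAP departs from Protocol 15.5.1 on the Phase 2a primary endpoint, does not list the departure, and contradicts itself on pooling. As written, it yields an ORR that can be compared with neither 45.25% nor 5%. The blended benchmark is 21.1% at planned sizes, and the same 18/60 supports opposite conclusions about the two arms.

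These figures assume exact two-sided 95% intervals and, for the 18/60 example, full accrual with Phase 1b patients left out. That ORR itself is pooled is read from SAP 4.2.1 and 4.2.6, because 4.8.1 is silent; no SAP text provides efficacy by arm. This should be corrected before the efficacy output is produced.

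**What to change.** - **SAP 4.2.1 and 4.8:** present best overall response, ORR, DCR, PFS and OS for Phase 2a separately for Arm I and Arm II. Give each arm's ORR with a Clopper-Pearson 95% interval beside its benchmark. Keep the dose-pooled summaries as supportive.
- **If an arm is short:** report the actual n and interval, and make no claim under the 17/24 or 6/36 rule.
- **SAP 4.2.3 and 4.2.6:** align both with the pooling and the by-arm analysis actually planned.
- **SAP section 5:** list and justify any remaining departure from Protocol 15.5.1.
- **Useful but optional:** responder counts by tumour type within arm, and Phase 1b responses by dose level and prior checkpoint-inhibitor exposure. Phase 1b cohorts are 3 or 6 patients, so these are counts only.

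The cost is SAP wording and extra table columns; no new data are needed, and the SAP already uses arm for exposure. The drawback is smaller denominators and wider intervals in each column.
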